1.0 Objectives

1.1 Study Objectives

The central hypothesis of the research study is that low dose naltrexone (LDN), in combination with hormonal suppression of endometriosis (standard of care), will lead to significant improvement of endometriosis-related pain. The proposal seeks to: 1) determine if the addition of LDN to standard endometriosis treatments will improve patient- reported endometriosis associated pain using daily 100-point Visual Analogue Scale (VAS) scores and 2) measure the impact of treatment on quality of life as measured by questionnaires including the Endometriosis Health Profile-30 (EHP30) and the Patient's Global Impression of Change (PGIC), and Patient Global Assessments (PGA) specific to pain, dysmenorrhea, and non-menstrual pelvic pain. We propose a double-blind placebo-controlled randomized clinical trial to achieve the following aims:

Aim 1: Identify the impact of LDN on daily endometriosis associated pain. We hypothesize that LDN in combination with standard hormonal suppression of endometriosis will decrease endometriosis associated pain reported using the VAS as compared with hormonal suppression alone.

Aim 2: Identify the impact of LDN on quality of life among women with endometriosis. The EHP30 and PGIC are surveys used to measure quality of life outcomes. We hypothesize that LDN in combination with standard hormonal suppression of endometriosis will improve quality of life as compared with hormonal suppression alone

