1.3 Secondary Study Endpoints

The secondary study endpoints will include the following quality of life measures:

- 1) Patient's Global Impression of Change (PGIC) surveys
- 2) Endometriosis Health Profile-30 (EHP 30) surveys
- 3) Patient Global Assessment (PGA)- pain, dysmenorrhea, non-menstrual pelvic pain

Additional secondary outcomes will include pain medication use (opioid and non-opioid). Subject reported daily analgesic use (NSAIDs and opioid) will be recorded and narcotic prescriptions will be verified using the state run Prescription Drug Monitoring Program monthly. Subject reported side effects to medications will also be monitored.

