2.3 Study Rationale

Naltrexone hydrochloride is a well-known, competitive opioid antagonist traditionally used to treat opioid overdose or addiction. At much lower doses, naltrexone has significantly different pharmacologic properties. Low-dose naltrexone (LDN) acts on non-opioid receptors in the central nervous system to decrease activation of microglial cells and decrease plasma levels of multiple inflammatory cytokines. LDN has also been shown to transiently block all three subtypes of opioid receptors (μ , κ , δ) resulting in an upregulation of not only opioid receptors, but also increasing endogenous opioid production. Early studies of LND in other inflammatory disorders, such as inflammatory bowel disease and fibromyalgia, have demonstrated promising results. Since the pelvic pain associated with endometriosis is due in part

to increased peritoneal inflammation, LND has the potential to provide non-narcotic analgesic relief by decreasing endometriosis-associated inflammation.

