The study will include a 12-week intervention period during which subjects will be asked to record daily electronic VAS scores, report daily analgesic use (NSAIDs and opioids) and complete surveys every 4 weeks. VAS scores will be reported daily. Patient Global Impression of Change (PGIC), Patient Global Assessments (for pain, dysmenorrhea, nonmenstrual pelvic pain and function) (PGAs) and Endometriosis Health Profile-30 (EHP 30) surveys will be completed at 4-week intervals during the intervention (0, 4, 8, and 12 weeks). Subjects will be asked to complete a brief telephone interview visit at 16 weeks to complete final quality of life surveys (EHP 30, PGAs and PGIC).

Subjects will be screened for side effects and asked to record pain medication use throughout the duration of the study. Subjects will be dispensed a 4-week supply of medications from the Investigational Pharmacy. They will be required to bring medication bottles to each visit for counting and drug accountability. Any remaining capsules will be returned to the pharmacy. All study subjects and investigators will remain blinded to the study group until the completion of the study. In the event subjects cannot attend study visits in-person due to extenuating circumstances (e.g. related to COVID-19 pandemic), remote visits can be completed via telephone for which questionnaires will be sent via REDcap and IDS will ship of study drug. Drug accountability and monitoring for side effects can also be done via telephone.

Procedure	Pre- screen	Screening Visit (beginning of Run-in week)	Visit 1 Enrollment – Randomization (Day 1)	Visit 2* 4-weeks (Day 28- 30)	Visit 3* 8-weeks (Day 56- 58)	Visit 4* 12-weeks (Day 84- 86)	Visit 5 16-weeks Phone f/u (Day 114- 121
Screening Criteria	Х						
Informed Consent		X					
WERF Questionnaire		Х					
Physical		Х					
Past Medical History		Х					
EHP-30		Х	Х	Х	Х	Х	Х
PGIC				X	X	X	Х
PGAs		Х	Х	Х	X	Х	Х
Study Drug Dispensed & Compliance		X (Only Norethindrone Acetate given, if needed)	Х	Х	Х	Х	
Daily Pain, Analgesic and Study Medication Assessment		X (6-7 days)	X (Daily)	X (Daily)	X (Daily)	X (Daily)	X (Daily)
Screening/Assessment of Adverse Events		X	Х	X	X	X	Х

Visit Table Summary of Study Procedures

(*) - these asterisked visits can be done remotely via telephone, if warranted due to extenuating circumstances.

7.2.1 Screening visit:

Screening Visit 1:

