Study subjects will receive education on analgesics approved for use in the study which are also within the standard of care for the management of pelvic pain associated with endometriosis. As standard of care for these patients, study subjects will be instructed to take ibuprofen as first time treatment and acetaminophen if additional pain relief is needed, both of which are available over the counter. Only if requested will a stronger medication be prescribed like oxycodone. If needed, to relieve pain, the subject will be advised to take first the ibuprofen 600 mg every 6 hours as needed for pain with food, then acetaminophen 1000mg every 6 hours as needed for pain. Subjects needing additional pain relief will need to discuss this with the study team in which oxycodone 5 mg every 6 hours as needed for pain will be prescribed. Refill prescriptions for opioid pain medication will be provided using the same dose and quantity beyond the screening visit on an as needed basis and will not be routinely provided at any subsequent study visits unless there is a documented need. The subject will complete an EPH-30 and PGAs surveys at the visit. The subject will be instructed to complete their daily surveys which include the VAS and medication compliance. We will also review and record any adverse events. At this time, we will also review compliance of daily reporting since the previous visit. Surveys will be sent via email through a secure link with RedCap and completed on-site during the visit.

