8.3 Statistical methods

The VAS scores will be collected daily from 1-week pre-intervention to 12 weeks postintervention. Prior to analysis, the AUC VAS scores will be calculated per participant separately for the 1-week pre-intervention period and the randomization to 12 weeks post-intervention period. Subsequently, the AUC VAS score data will be normalized per participant to an average AUC VAS score per week (i.e., 7 days) to account for participants that withdraw early from the study. The primary outcome of interest is the AUC VAS scores from randomization to 12 weeks post-intervention period. For this primary outcome, a linear mixed-model will be used to compare the average AUC VAS scores from randomization to 12 weeks post-intervention between the two intervention groups, adjusting for the covariate of opioid intake during the 12-week trial as measured in morphine equivalent units (MEUs)) and using the subject as a random effect in the model.

A secondary analysis with AUC VAS scores as the outcome will use a linear mixed-effects model having intervention group, the repeated factor of time period (1-week pre-intervention and randomization to 12 weeks post-intervention), the interaction of intervention group and time period, and the covariate of opioid intake during the trial as fixed effects and the participant as a random effect. Contrasts will be constructed from this mixed model to compare within and between the intervention groups with respect to AUC VAS scores. Similarly, linear mixed-effects models will be used to compare the two interventions over time with respect to the outcomes of PGIC and EHP30 which are collected at 4-week intervals over the course of the trial. Another secondary analysis will fit a linear random coefficients model to the weekly VAS scores (i.e., not AUC) to generate linear trajectories for each intervention group, adjusting for the covariate of opioid intake. From these trajectories, estimates for the rate of change (i.e., slope) over time in VAS scores will be compared between the two intervention groups. In the event linear trajectories do not fit the data well, higher order polynomials (e.g., quadratic) will be considered to estimate the curve trajectory per intervention.

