12.0 Potential Benefits to Subjects and Others

12.1 Potential Benefits to Subjects

The potential benefits to subject may be a decrease in pain and narcotic use.

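### The primary model adjusts for opioid intake during the trial, a post-randomisation outcome, so it does not estimate the effect of assignment that Aim 1 asks for

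*Combined protocol and SAP*

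**What the plan says.** Section 8.3 gives one primary model: a linear mixed model comparing AUC VAS from randomisation to week 12 between arms, "adjusting for the covariate of opioid intake during the 12-week trial as measured in morphine equivalent units". The secondary AUC model (group, period and their interaction) includes "the covariate of opioid intake during the trial as fixed effects", and the slope model for weekly VAS also adjusts for opioid intake. I found no version of the primary comparison without this term, and no stated reason for including it.

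Elsewhere the protocol treats opioid use as something the trial may change:

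- Aim 1 (section 1.1) hypothesises that LDN added to hormonal suppression "will decrease endometriosis associated pain reported using the VAS as compared with hormonal suppression alone". Section 1.2 defines the primary endpoint as the VAS difference between groups.
- Section 1.3: "Additional secondary outcomes will include pain medication use (opioid and non-opioid").
- Section 7.2.2: if more relief is needed after ibuprofen and acetaminophen, "oxycodone 5 mg every 6 hours as needed for pain will be prescribed".
- Section 12.1: "The potential benefits to subject may be a decrease in pain and narcotic use".
- Section 2.3: "LDN has also been shown to transiently block all three subtypes of opioid receptors".

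**The concern.** Randomisation protects a comparison adjusted for variables fixed before assignment. It does not protect one adjusted for a variable that assignment may alter. Here a woman's opioid intake can respond to her pain, and so to LDN through pain. It can also respond to LDN directly, since the drug acts on opioid receptors.

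The planned coefficient answers whether pain differs between arms among women with the same opioid intake. Aim 1 asks whether adding LDN lowers pain. If LDN lowers both pain and opioid use, which is the result the trial hopes for, the model credits part of the pain reduction to the lower opioid use and removes it from the treatment effect. If LDN changes opioid use by a route other than pain, the model can show a pain difference that does not exist. The direction depends on whether intake rises or falls and on the sign of its correlation with recorded pain.

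**Working it through.** **Inputs from section 8.2.** Difference 10 mm, SD 20 mm (standardised effect 0.5), two-sided 0.05, 80% power, 20% withdrawal, 160 randomised.

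**Assumptions, not in the documents.** The within-arm correlation r between opioid intake M and AUC VAS, and the effect of LDN on M. Everything from step 2 on is illustration across a range of these.

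**1. The plan's own figure.** A two-sample t-test at effect size 0.5 needs 63.8, so 64 per arm. Then 64 / 0.8 = 80 per arm, or 160. Power with 64 completers per arm is 80.1%. The stated size reproduces, and it is for the plain difference in means with no covariate.

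**2. Intake driven by pain.** In a linear model with arm and M,

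adjusted effect = total effect − (within-arm slope of pain on M) × (effect of LDN on M).

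Scale M to SD 1. The slope is 20r mm per SD. A 10 mm fall in pain (0.5 SD) lowers M by 0.5r. So the adjusted effect is 10 − 20r × 0.5r = 10(1 − r²). Power comes from 12,000 simulated trials per value.

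| r | adjusted effect | power |
|---|---|---|
| 0.1 | 9.9 mm | about 80% |
| 0.3 | 9.1 mm | about 76% |
| 0.5 | 7.5 mm | about 67% |
| 0.7 | 5.1 mm | about 51% |

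**3. Sparse use.** Let only 10 / 25 / 50% of control women take any opioid, with M = max(pain z-score + noise − threshold, 0).

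- Tighter link to pain (noise SD 1): 9.0 / 7.9 / 6.6 mm, power about 75 / 70 / 62%.
- Looser link (noise SD 2): 9.6 / 9.1 / 8.6 mm, power about 78 / 76 / 74%.

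**4. No effect on pain, LDN changes intake by another route.** The false difference is r × 20 × shift in SD.

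| r | change in intake | false difference | rejection (nominal 5%) |
|---|---|---|---|
| 0.1 | −0.3 / −0.5 SD | 0.6 / 1.0 mm | 5% / 6% |
| 0.3 | −0.3 / −0.5 SD | 1.8 / 3.0 mm | 8% / 14% |
| 0.5 | −0.3 / −0.5 SD | 3 / 5 mm | 16% / 35% |

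At r = 0.3 and 0.5 nearly all of these rejections go against LDN. The sign reverses, giving a spurious benefit, if r is negative (r = −0.5: again 3 / 5 mm and 16% / 35%) or if LDN raises intake (r = 0.5, +0.5 SD: about 5 mm, about 35%).

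**5. LDN does not change intake.** No bias: the effect stays at 10 mm and power rises to 83% / 90% at r = 0.3 / 0.5.

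**6. Secondary models.** If M is one value per participant, it cancels from the group-by-period interaction. In 60 simulated complete datasets at r = 0.5 the interaction was the same with and without M. The between-arm contrasts within each period did move: the pre-intervention one from 0.0 to 1.6 mm, and the post-randomisation one from −9.5 to −7.9 mm. The first is a difference between arms before any study drug was taken. The slope model is affected if M enters as a weekly time-varying covariate, and possibly with unbalanced data; section 8.3 does not say how it enters.

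**The case against.** The strongest defence is that rescue opioids can mask pain, so arms should be compared at like opioid use. The aim is legitimate, but this adjustment does not achieve it. Correcting for masking needs a negative coefficient on intake, whereas as-needed use tends to give a positive one, because women in more pain take more. Suppose the effect without rescue is 10 mm, each SD of intake lowers VAS by 0.2 SD (4 mm), and r = 0.5. Intake falls by 0.25 SD, so the unadjusted effect is 10 − 4 × 0.25 = 9.0 mm. The adjusted effect is 7.5 mm, further from 10.

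Second, opioid use may be light: section 3.2 excludes chronic daily users, and section 7.2.2 provides oxycodone only on request. This limits the illustrations. In the sparse-use model mean control intake is about 0.25 / 0.42 / 0.68 SD at 10 / 25 / 50% users. A 0.5 SD fall is therefore impossible at 10% or 25% users, and a 0.3 SD fall is impossible at 10% and needs a cut of about 71% at 25% (0.3 / 0.42). With a 50% cut and no pain effect, rejection is about 6% at 10% users, 7 to 13% at 25%, and 14 to 38% at 50%. The larger false-positive figures need common opioid use.

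Third, the group-by-period interaction in the secondary model escapes the problem if intake is a single trial total. That is the natural reading, but not a stated one: analgesic use is also recorded in the run-in, and period-specific intake would not cancel. Even where it holds, that contrast is secondary.

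**Conclusion.** The concern holds. The only primary model conditions on a post-randomisation variable that the protocol itself lists as an outcome, so it does not estimate the effect of assignment stated in Aim 1 and powered in section 8.2. It is free of bias only if LDN leaves opioid intake unchanged, which sections 1.3 and 12.1 treat as an open question.

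The size and direction of any bias cannot be derived from the documents. Under the assumed ranges it runs from negligible (9.9 mm for a true 10 mm at r = 0.1) to severe (5.1 mm and about 51% power at r = 0.7). Test size can exceed 5% if LDN changes intake by a route other than pain. Because this is the primary test, it should be corrected before unblinding. I am highly confident of the principle; the magnitudes are illustrative.

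**What to change.** Before unblinding, amend section 8.3 as follows.

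1. Remove on-trial opioid intake from the primary model and from the between-arm contrasts in the secondary AUC model.
2. Adjust only for variables measured before randomisation: run-in AUC VAS, which section 8.3 already calculates, and, if wanted, run-in opioid intake from the diary (visit table in section 7.1, row "Daily Pain, Analgesic and Study Medication Assessment").
3. Compare opioid intake by arm as the secondary outcome already named in section 1.3.
4. Keep the opioid-adjusted model as a prespecified, labelled sensitivity analysis. State whether intake is a trial total or a weekly rate; weekly normalisation is specified for AUC only.
5. State how intake enters the slope model and the group-by-period model, and remove it wherever it varies over time. Say whether the PGIC and EHP-30 models carry it.
6. State how rescue opioid use is handled in the primary comparison. Items 1 to 3 correspond to counting it as part of the treatment effect; the plan should say so.

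**Cost.** A change of text to the primary analysis in the protocol, with no new data or patients and no change to 160. If LDN does not affect intake, the precision from the on-trial covariate is given up (80% power rather than 83% / 90% at r = 0.3 / 0.5). Run-in AUC VAS would recover the same gain if it correlates equally with the outcome. The VAS result must also be read beside the opioid comparison, because equal pain with fewer opioids would appear as no difference on the primary endpoint.

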8.2 Sample size determination

The primary outcome will be the average area under the curve (AUC) as determined by the daily VAS scores collected per participant over the course of the trial. Previous studies have demonstrated that a 10 mm change in VAS scores and demonstrated a standard deviation of 20 mm. Using these previously published data as a guide for our sample size estimation, we believe a standardized effect size (i.e., the difference in the AUC VAS score means between the two intervention groups divided by the standard deviation) of 0.5 will be clinically relevant to detect. Furthermore, based on our prior research with endometriosis patients, we anticipate a withdrawal rate of 20%. Therefore, we propose a target sample size of 160 (80 per intervention) randomized participants for this trial. Such a sample size yields 80% statistical power with a two-sided, 0.05 significance level test to detect a standardized effect size of 0.5, while accounting for the 20% withdrawal rate. The true statistical power actually may exceed 80% because our statistical methodology will include partial data for those participants who withdraw (up to the point in time at which they withdraw).

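### The two-period secondary AUC model in 8.3 leaves the period variances unspecified and the baseline arm means free, so its group-by-period contrast loses precision and its single-period arm contrasts may be miscalibrated

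*Combined protocol and SAP*

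**What the plan says.** Section 8.3 computes two AUC values per woman: "the AUC VAS scores will be calculated per participant separately for the 1-week pre-intervention period and the randomization to 12 weeks post-intervention period". Each is then "normalized per participant to an average AUC VAS score per week (i.e., 7 days"). That puts the two values on one scale, although one averages about 7 diary days and the other up to 84.

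The secondary AUC model takes both values as the outcome. Its fixed effects are arm, "the repeated factor of time period (1-week pre-intervention and randomization to 12 weeks post-intervention"), the arm-by-period interaction and opioid intake during the trial. The only random term is the participant. No residual covariance or period-specific variance is given, and nothing ties the arms to the same pre-intervention mean. On what will be reported, the section says "Contrasts will be constructed from this mixed model to compare within and between the intervention groups with respect to AUC VAS scores"; the contrasts are not listed.

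The primary model uses only the post-randomization AUC, adjusts for opioid intake, and has no baseline term.

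**The concern.** With two records per person, one participant random effect and one residual variance imply equal total variance in both periods. A mean of 7 days is normally noisier than a mean of 84. The run-in is also a transition week, because women on oral contraceptives or GnRH agents are switched to norethindrone acetate then (3.1). A between-arm contrast taken at one period would use the pooled variance, which fits neither period if the two differ.

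Separately, baseline enters as an outcome with free arm means, so the interaction subtracts the noisy run-in week in full. Adjusting for it would use only as much of it as predicts the later score. What is at stake is the calibration of some secondary intervals, and precision in the AUC analysis that explicitly sets the run-in week against treatment.

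**Working it through.** **1. The plan's own figure.** Section 8.2 gives 10 mm, SD 20 mm (effect 0.5), two-sided 0.05, 80% power and 20% withdrawal. By the normal approximation, 2(1.96+0.84)²/0.5² gives 63 per arm; the t-test needs 64 (power 0.801). Then 64/0.8 = 80 per arm, or 160. The figure reproduces. The plan states no figure for the two-period model.

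**2. Formulas.** Let sb, sd and sw be the between-person, day-to-day and week-to-week SDs. All are assumptions: sb 15 to 18, sd 15 to 25, sw 0 to 10. The opioid covariate is left out.

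- Run-in variance: v1 = sb² + sd²/7 + sw²
- 12-week variance: v2 = sb² + sd²/84 + sw²/12
- Pooled variance: m = (v1+v2)/2
- 12-week arm contrast, model SE over true SE: √(m/v2)
- Baseline arm contrast, model SE over true SE: √(m/v1)
- Group-by-period SE over baseline-adjusted SE: √[(v1+v2−2sb²)/(v2−sb⁴/v1)]

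**3. Results at the ends of the range.**

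| sb, sd, sw | v1 | v2 | 12-week ratio | Baseline ratio | Change vs adjusted |
|---|---|---|---|---|---|
| 18, 15, 0 | 356.1 | 326.7 | 1.022 | 0.979 | 1.044 |
| 15, 25, 10 | 414.3 | 240.8 | 1.166 | 0.889 | 1.315 |

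So the 12-week SE is 2% to 17% too wide, the baseline SE 2% to 11% too narrow, and the group-by-period SE 4% to 32% larger than the adjusted one.

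These inputs give a 12-week SD of 15.1 to 18.4, below the plan's 20 mm (whose averaging period is not stated). Choosing sb so that v2 = 400, with sd and sw over the same ranges, narrows the results to 2% to 10% for the 12-week SE and 4% to 20% for the precision loss.

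**4. One case in full.** Assume run-in SD 24, 12-week SD 20, correlation 0.6 and 64 per arm, so √(2/64) = 0.1768.

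- 12-week arm contrast: true SE 20 × 0.1768 = 3.54; model SE √((576+400)/2) × 0.1768 = 3.91, about 10% too wide.
- Baseline arm contrast: true SE 24 × 0.1768 = 4.24; model SE 3.91, 8% too narrow.
- Group-by-period: √(576+400−2×0.6×24×20) × 0.1768 = 20 × 0.1768 = 3.54.
- Baseline-adjusted: 20 × √(1−0.36) × 0.1768 = 2.83. The ratio is 1.25, and power for 10 mm is 81% against 94%.

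**5. Simulation of that default model (300 trials per scenario).**

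| Run-in SD, correlation | Contrast | Mean SE | Empirical SD | Coverage |
|---|---|---|---|---|
| 24, 0.6 | Group-by-period | 3.52 | 3.37 | 95.0% |
| 24, 0.6 | 12-week arms | 3.88 | 3.64 | 96.7% |
| 24, 0.6 | Baseline arms | 3.88 | 4.31 | 92.7% |
| 26, 0.5 | Group-by-period | 4.16 | 4.22 | 95.7% |
| 26, 0.5 | 12-week arms | 4.10 | 3.88 | 96.3% |
| 26, 0.5 | Baseline arms | 4.10 | 4.87 | 89.3% |

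The group-by-period results were identical to a change-score analysis. With equal SDs of 20, all three contrasts covered at about 95%.

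**6. Can the direction reverse?** Yes. Add an assumed between-person response SD of 10 mm to v2, with sb 18 and sd 15. The 12-week ratio is then √(391.4/426.7) = 0.96 with no weekly fluctuation, and 1.01 with sw 10.

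**The case against.** A reader might infer that the plan imposes equal variances and that its intervals are therefore wrong and too wide. The documents do not support that, for these reasons.

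- Equal variance is the default result of a lone participant effect. Section 8.3 does not state it as a rule, and its wording leaves room for period-specific variances.
- Within-arm change and group-by-period contrasts depend only on within-person differences. Their standard errors stay valid when the period variances differ, as the simulated coverage shows.
- Too wide is not general. When the run-in variance is larger, the baseline contrast is too narrow. If women differ in response, which is plausible with individual norethindrone adjustment (7.1), the 12-week error can vanish or reverse.
- The primary model already compares arms on the post-randomization AUC without pooling in baseline variance, and a baseline arm contrast is not an efficacy result.
- Baseline is not ignored, because the interaction subtracts it. Nor is this clearly the only analysis to use the run-in week: the weekly random coefficients model does not exclude it.

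It is also tempting to say that randomization guarantees equal baseline means in this model. It makes them equal in expectation without conditioning. Here the model conditions on opioid intake during the trial. If treatment alters opioid use, adjusted baseline means can differ by arm.

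All of this stands and narrows the point. It does not answer the lost precision of the change-type contrast, the unstated covariance, or the unlisted contrasts.

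**Conclusion.** The point holds as a modest improvement to a secondary analysis. Fitted in the default way, the model gives a valid but inefficient group-by-period contrast, with an SE about 4% to 32% above a baseline-adjusted one. If the variances differ, its single-period arm contrasts are miscalibrated. With the run-in week the more variable, the 12-week SE is about 2% to 17% too wide and the baseline SE too narrow; with the post period the more variable, the signs swap.

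Every size depends on assumed SDs, on complete 84-day diaries and on leaving out the opioid covariate. The documents give one SD, 20 mm, and do not say which average it describes. The precision loss does not need unequal variances: with equal SDs and correlations of 0.3 to 0.8 the change-score SE is still 5% to 24% larger. The sample size of 160 and the primary test are unaffected.

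**What to change.** In 8.3, replace the single participant random effect in the two-period model with an unstructured 2x2 covariance for the run-in and post-randomization AUC. Name one result: the baseline-adjusted 12-week between-arm contrast. Obtain it in one of two ways:

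- constrain the arms to a common pre-intervention mean; or
- model the 12-week AUC with the run-in AUC as a covariate.

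If the common-mean constraint is chosen, apply it in a fit without during-trial opioid intake, since randomization justifies the constraint only when that later variable is not conditioned on.

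The cost is a few lines of SAP text and model code, with no new data. It should be settled before unblinding, so that the contrast is not chosen after the results are seen.
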